Preregistration on Clinicaltrials.gov

Project:

„Hypnosis Induction and Height Experience in VR - Control Group Comparison and Three Sessions“

Unique Protocol ID: 521/2019BO2

Description of the Hypotheses, Analyses and needed Sample Sizes

06.05.2024

1. Data collection. Have any data been collected for this study already?

No data has been collected for this study.

2. Hypothesis: What's the main question being asked or hypothesis being tested in this study?

- a. Do three sessions of VR therapy reduce the fear of heights in both groups?
 - i. We expect a decrease in fear of heights over the sessions.
 - ii. Fear of heights decreases over the three sessions, with the experimental group benefiting more from the sessions than the control group.
- b. The fear of heights increases less from after the last therapy session to the follow-up measurement after one week in the experimental group than in the control group.
- c. Does the anxiety experience curve change during the VR height confrontation over the three sessions in both groups?
 - i. We expect typical anxiety experience curves according to the habituation (linear increase in anxiety and quadratic decrease).
 - ii. We expect a decrease of the mean anxiety experience rating over the sessions.
 - iii. We expect that the anxiety experience curves rise less sharply with each session.
 - iv. We expect that the anxiety experience curves reach their turning point earlier with each session.
 - v. The experimental group has lower anxiety experience ratings across all sessions and rises (20 ascents during the height confrontation) compared to the control group.
- d. How does a person's suggestibility influence the perception and impact of the intervention?
 - i. More suggestible people show a greater reduction in anxiety over the three sessions than less suggestible people.
 - ii. The influence of suggestibility on the strength of reduction in anxiety over the three sessions is stronger in the experimental group than in the control group.
 - iii. Suggestibility and group affinity interact such that in the experimental group participants with higher suggestibility show a lower level of anxiety experience during the height confrontation than less suggestible participants, but in the control group higher suggestible participants exhibit greater anxiety experience during the height confrontation than less suggestible participants.

3. Analyses

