The analyses are carried out using linear mixed models. Each model is tested with the car::Anova() function (model comparison Typ II ANOVA) in R to determine the significance of the individual effects. The model equations are written down below and the abbreviations used for the effects are explained.

grp: experimental vs. control group (enters model equation as factor: experimental

group is reference group)

sugg: suggestibility (enters model equation as linear predictor)

a. HIQ ~ grp + sess + grp:sess + (1 | id)

sess: baseline vs. post first session vs. post second session vs. post third session (enters model equation as factor)

For hypothesis a(i) we investigate the significance of sess.

For hypothesis a(ii) we investigate the significance of grp:sess.

b. HIQ ~ grp + sugg + mtp + sugg:mtp + grp:sugg + grp:mtp + grp:sugg:mtp + (1 | id)

mtp: measurement time point, baseline vs. post third session (enters model equation as factor)

For hypothesis d(i) we investigate the significance of sugg:mtp.

For hypothesis d(ii) we investigate the significance of grp:sugg:mtp.

c. HIQ ~ grp + mtp + grp:mtp + (1 | id)

mtp: measurement time point, post third session vs. one-week follow-up (enters model equation as factor)

For hypothesis b we investigate the significance of grp:mtp.

d. fear ~ grp + sugg + sess + rise + rise^2 + grp:sugg + sess:rise + sess:rise^2 + (rise + rise^2 | id)

sess: first session vs. second session vs. third session (enters as linear predictor)

rise: 20 rises during each of the three sessions, these are entered as a centered variable into the model equation (centered at total mean)

For hypothesis c(i) we investigate the significance of rise and rise^2.

For hypothesis c(ii) we investigate the significance of sess.

For hypothesis c(iii) we investigate the significance of sess:rise.

For hypothesis c(iv) we investigate the significance of sess:rise^2.

For hypothesis c(v) we investigate the significance of grp.

For hypothesis d(iii) we investigate the significance of grp:sugg.

4. Sample Size

- a. Analysis a needs 56 participants to achieve a Power of 80% for the effects of interest.

- b. Analysis **b** needs 92 participants to achieve a Power of 80% for the effects of interest.
- c. Analysis **c** needs 60 participants to achieve a Power of 80% for the effects of interest.
- d. Analysis **d** needs 50 participants to achieve a Power of 80% for the effects of interest.

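### Model d's linear session term rests on session 3 minus session 1, so it cannot by itself support the each-session wording of c(iii) and c(iv)

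*SAP*

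**What the plan says.** SAP section 2 states c(iii) as "We expect that the anxiety experience curves rise less sharply with each session" and c(iv) as "We expect that the anxiety experience curves reach their turning point earlier with each session". Both describe what happens at each step, from session 1 to 2 and from session 2 to 3.

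Section 3, analysis d, gives the model as "d. fear ~ grp + sugg + sess + rise + rise^2 + grp:sugg + sess:rise + sess:rise^2 + (rise + rise^2 | id" and codes session as "sess: first session vs. second session vs. third session (enters as linear predictor". The decision rules are "For hypothesis c(iii) we investigate the significance of sess:rise" and "For hypothesis c(iv) we investigate the significance of sess:rise^2". Testing is by Type II analysis of variance on each term: "Each model is tested with the car::Anova() function (model comparison Typ II ANOVA) in R to determine the significance of the individual effects".

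Analysis a, on HIQ, codes session differently: "sess: baseline vs. post first session vs. post second session vs. post third session (enters model equation as factor".

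For the in-session anxiety ratings, the SAP lists no contrast between adjacent sessions, no non-linear session term and no check of linearity. The per-session exploratory analysis in section 5b(i) uses HIQ before and after each session, not the anxiety curves.

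**The concern.** The hypotheses and the test do not ask the same thing. Each hypothesis speaks of two steps. The test gives session one straight-line coefficient per curve component, which describes only the net change from first to last session.

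A significant coefficient could be reported as support for change at each session in three different situations: an even change, a change confined to one step with nothing at the other, and a reversal at session 2 followed by a larger change at session 3. Question c asks how the curve changes over three sessions, so whether the third session still adds anything is a natural reading of a positive result. The planned test cannot show it.

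**Working it through.** **Inputs from the SAP.** Three sessions, 20 rises per session, rise centered, session numeric, fixed terms sess, sess:rise and sess:rise^2, and random intercept, rise and rise^2 per participant (section 3, analysis d). Section 4 gives 50 participants for 80% power in analysis d. The SAP states no effect sizes or variances behind that figure, so it cannot be reproduced; the point does not depend on it.

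**Step 1: what the coefficients estimate.** Code session as s = -1, 0, +1 (shifting the code leaves the interaction coefficients unchanged). Let b1, b2, b3 be the rise slopes fitted within sessions 1, 2 and 3. With complete ratings:

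sess:rise = Σ s·b / Σ s² = (-b1 + 0·b2 + b3) / (1 + 0 + 1) = (b3 - b1) / 2

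The same formula holds for sess:rise^2 with the quadratic coefficients. The participant-level random effects are constant over sessions and cancel from this contrast, so the weights do not depend on the variances. Building the full design for 50 participants and solving by generalised least squares gave weights of -0.5, 0.0 and +0.5 for both terms.

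**Step 2: patterns the test cannot separate.** The values are illustrative, not from the SAP.

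| Pattern | Rise slope, sessions 1, 2, 3 | sess:rise | rise^2 coefficient, sessions 1, 2, 3 | sess:rise^2 |
|---|---|---|---|---|
| Even change | 0.10, 0.08, 0.06 | -0.02 | -0.010, -0.012, -0.014 | -0.002 |
| All change at step 1 to 2 | 0.10, 0.06, 0.06 | -0.02 | -0.010, -0.014, -0.014 | -0.002 |
| Session 2 contradicts | 0.10, 0.14, 0.06 | -0.02 | -0.010, -0.004, -0.014 | -0.002 |

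In each row (0.06 - 0.10)/2 = -0.02 and (-0.014 + 0.010)/2 = -0.002.

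The turning point in rises is 10.5 - b_rise/(2·b_rise^2). Row 1 gives 15.5, 13.8 and 12.6, earlier each time. Row 3 gives 15.5, 28.0 and 12.6: in session 2 the turning point moves beyond the last of the 20 rises, yet sess:rise^2 is unchanged.

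**Step 3: how often the rule confirms.** Assumptions: 50 participants, residual SD 1.5, random-effect variances 4, 0.01 and 0.0001, two-sided 5% test, 400 simulated trials per pattern.

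- c(iii), even change: significant in the predicted direction in 94.5%.
- c(iii), session 2 contradicts: 95.0%.
- c(iv), same two patterns: 44.8% and 40.8%.
- c(iii) with a session 2 slope of 0.30: 87.8%. Session 2 has entered the residual variance, but the estimate has not moved.

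**Step 4: dropout.** The SAP expects about 10% (section 4). The session 2 weight becomes 0.024 to 0.026 if 10% miss session 3, 0.052 to 0.056 if 20% miss session 3, and 0.004 to 0.009 if 10% miss sessions 2 and 3. It stays small beside weights near 0.5.

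**Step 5: power of single steps.** Set the session 1 to 3 slope change at 2.8 standard errors: power = Φ(2.8 - 1.96) = Φ(0.84) = 80%. With complete data each step difference has the same standard error, so under an even decline one step is 1.4 standard errors: power = Φ(1.4 - 1.96) = Φ(-0.56) = 29%. The two step estimates share session 2 with opposite sign, so they correlate at -0.5. The bivariate normal probability that both pass is 2.9%. Raising it to 80% would need about 3.24 standard errors per step, or (3.24/1.4)² ≈ 5.4 times the sample.

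**The case against.** The strongest reply is that this is a matter of wording. Any linear trend over three equally spaced levels has weights -1, 0, +1. The SAP discloses the coding, the parent question c asks about change over the three sessions, and the each-session phrase can be read as an average rate per session, which is what a linear coefficient estimates. Much of this stands: a prespecified linear trend is a legitimate test of overall change. What remains is that c(iii) and c(iv), unlike c(ii), are worded by step, and a positive trend test does not license that wording.

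The comparison with analysis a also proves less than it seems to. A four-level factor under an analysis of variance gives an omnibus test, which can itself be significant when one session reverses. Factor coding helps only if the step differences are then estimated.

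A reader might go further in three ways, none of which the SAP supports.

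- That c(ii) fails as well. It rests on the same linear session term, but it predicts only a decrease over the sessions as a whole, which a trend fits.
- That session 2 plays no part at all. The zero weight concerns the estimates with complete data. Session 2 still enters the residual variance, and with dropout its weight is small but not zero.
- That c(iii) and c(iv) should stand only if both steps are significant. Nothing in the SAP implies this, and it would reject a true even decline in about 97% of trials under the Step 5 assumptions.

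**Conclusion.** The concern holds for c(iii) and c(iv) only. With complete ratings, the coefficients that decide them are exactly half the session 3 minus session 1 difference, whatever the variances. The decision rule cannot distinguish change at each session from change at one step or from a reversal at session 2, and no listed analysis of the ratings would reveal the difference. The confirmation rates in Step 3 depend on assumed variances and illustrative slopes; the zero weight does not. The trend test is sound as a test of overall change, so the fault lies in the claim attached to it. The point is worth settling in the SAP, which states that no data had been collected.

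**What to change.** 1. Keep the linear sess:rise and sess:rise^2 tests as the decisive tests of overall change. Word a positive result as a change *from the first to the third session*, or restate c(iii) and c(iv) as a trend over sessions.
2. Refit model d with session as a three-level factor. Report the session 2 minus 1 and session 3 minus 2 differences, with confidence intervals, for the rise slope and for the turning point. Derive the turning point from the rise and rise^2 coefficients together, because the rise^2 coefficient alone does not locate it.
3. State that the change occurred with each session only if these estimates support it. Do not require both steps to be significant.

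Cost: SAP wording and one extra fit, with one more fixed-effect term each for sess, sess:rise and sess:rise^2. No new data are needed, and because the decisive tests stay as they are, the sample size for analysis d need not change on this account. The downside is a narrower claim from the trend test, with step estimates that will be imprecise.

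### Hypothesis c(iv), an earlier turning point with each session, is tested on the session change in curvature alone, which does not fix where the turning point lies or which way it moves

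*SAP*

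**What the plan says.** Section 2, c(iv), is a directional statement about location: "We expect that the anxiety experience curves reach their turning point earlier with each session". Its neighbour c(iii) concerns steepness: "We expect that the anxiety experience curves rise less sharply with each session".

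Section 3, model d, is "fear ~ grp + sugg + sess + rise + rise^2 + grp:sugg + sess:rise + sess:rise^2 + (rise + rise^2 | id" with its closing bracket. Session is coded as "sess: first session vs. second session vs. third session (enters as linear predictor", and the 20 rises are described thus: "these are entered as a centered variable into the model equation (centered at total mean". The two interactions are allotted separately: "For hypothesis c(iii) we investigate the significance of sess:rise", and "For hypothesis c(iv) we investigate the significance of sess:rise^2".

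The decision procedure for every model is: "Each model is tested with the car::Anova() function (model comparison Typ II ANOVA) in R to determine the significance of the individual effects". For c(iv) the SAP computes no turning point, requires no sign and gives no rule for reading sess:rise^2 together with sess:rise.

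**The concern.** The turning point of a quadratic is a ratio of its linear to its quadratic coefficient. Model d lets session change both, yet c(iv) is judged on the quadratic part alone. If sess:rise^2 does not determine the direction of the shift, the planned test answers a different question from the one posed. The trial could then report an earlier peak that did not occur, or fail to see one that did.

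**Working it through.** **The plan's own figure.** The SAP states 50 participants for 80% power in analysis d. This cannot be reproduced, because no effect size, variance or significance level is given. The argument below does not depend on it.

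**Algebra.** Number the rises 1 to 20, so the centre is 10.5, and the sessions s = 1, 2, 3. Let B1, B2, G1, G2 be the coefficients of rise, rise^2, sess:rise and sess:rise^2. In session s the linear coefficient is B1 + G1·s and the curvature coefficient is B2 + G2·s. The turning point is

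T(s) = 10.5 − (B1 + G1·s) / (2(B2 + G2·s)).

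Its rate of change with session is

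dT/ds = D / (2(B2 + G2·s)²), with D = B1·G2 − G1·B2.

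The denominator is positive, so the sign of D alone gives the direction, and it covers both session steps. The turning point is a peak only if B2 + G2·s < 0. Two consequences follow:

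- With G2 = 0, B2 < 0 and G1 < 0, D = −G1·B2 is negative. The peak moves earlier, but the planned test has nothing to detect.
- With G2 ≠ 0, D may be negative, zero or positive.

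Centring does not help. Moving the origin of rise by c replaces B1 by B1 − 2c·B2 and G1 by G1 − 2c·G2; the added terms cancel in D, and G2 is unchanged. Moving the origin of session by m replaces B1 by B1 + m·G1 and B2 by B2 + m·G2, and D is again unchanged.

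**Numerical examples (assumed coefficients).**

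| B1 | G1 | B2 | G2 | Peak, sessions 1/2/3 | D |
|---|---|---|---|---|---|
| 0.26 | −0.08 | −0.04 | +0.01 | 13.5 / 13.0 / 11.5 | 0.0026 − 0.0032 = −0.0006 |
| 0.20 | −0.05 | −0.04 | +0.01 | 13 / 13 / 13 | 0.0020 − 0.0020 = 0 |
| 0.14 | −0.02 | −0.04 | +0.01 | 12.5 / 13.0 / 14.5 | 0.0014 − 0.0008 = +0.0006 |
| 0.24 | −0.06 | −0.02 | 0 | 15 / 13.5 / 12 | 0 − 0.0012 = −0.0012 |
| −0.02 | +0.06 | 0 | −0.01 | 12.5 / 13.0 / 13.2 | 0.0002 − 0 = +0.0002 |

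The first three rows share the same sess:rise^2 and a negative sess:rise, yet the peak moves earlier, stays and moves later.

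**Simulation.** Balanced data, N = 50, 4,000 runs per cell. Assumed random SDs were 1.5 (intercept), 0.1 (rise) and 0.01 (rise^2), with residual SD 1, 2 and 3. The 5% level for the planned test is also assumed; the test of D < 0 is one-sided at 2.5%.

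| True peak | Planned test significant | D < 0 significant |
|---|---|---|
| 15 to 12, constant curvature | 4.8–5.0% | 88.6–100% |
| fixed at 13 | 99.5–100% | 2.3–2.6% |
| 12.5 to 14.5 | 99.3–100% | 0.0% |

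A check with lme4 and car::Anova type II (residual SD 2, 200 runs each) gave 4.5%, 100% and 100% for the planned test, and 100%, 3.5% and 0% for D.

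**The case against.** The strongest defence is a joint reading. c(i) expects a concave curve and c(iii) a falling linear term. If the linear coefficient at the centre is positive in every session, G1 < 0 together with G2 < 0 does imply an earlier peak. For example, (B1, G1, B2, G2) = (0.12, −0.02, −0.015, −0.003) gives 13.28, 12.40, 11.75. That is correct, but it needs a sign rule, a joint rule and a peak after the middle rise, and the SAP states none of these for c(iv). With a peak before the middle, (−0.10, −0.01, −0.015, −0.003) also has both interactions negative, yet the peak moves later: 7.44, 7.64, 7.79. And if sess:rise^2 is positive, the signs leave the direction open.

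Three further objections stand in part:

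- *Blindness at every sample size* holds only when G2 is exactly zero. With any other G2 rejection rises with N, but it does so whichever way the peak moves.
- *The near-100% rates reflect a large assumed effect.* The curvature coefficient falls threefold, from −0.03 to −0.01. For residual SD 1 to 3, the standard error of G2 at N = 50 is about 0.00075 to 0.0023, so G2 = 0.01 lies about 13 to 4.4 standard errors from zero. The rates show what can happen, not how often it will.
- *The replacement has less power and adds a condition.* In the first example (13.5 to 11.5), power for D was 31–78% at N = 50 and 54–97% at N = 100, for residual SD 3 to 1. This is a real cost. The condition on curvature binds little in these examples. In the flattest session (−0.01) with residual SD 3, the variance of the fitted curvature is 0.01²/50 + 9 × (1/3 + 1/2)/(17,556 × 50) = 0.0000105, where 17,556 = 20 × 399 × 396/180 is the sum of squares of rise^2 about its mean. The standard error is about 0.0032, so the curvature lies about 3 standard errors below zero.

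**Conclusion.** The concern holds. The test named for c(iv) does not test c(iv): significance of sess:rise^2 is neither necessary nor sufficient for an earlier turning point. This rests on algebra from the SAP's own model and needs no assumed figure; the coefficients, SDs and significance level only illustrate the size. The effect is confined to one of eleven listed hypotheses and leaves the HIQ analyses and the group test in c(v) untouched. It should be fixed, and the SAP says that no data had been collected when it was written.

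**What to change.** Keep model d. For c(iv), replace the significance of sess:rise^2 by a one-sided test of D = B1·G2 − G1·B2 < 0, by the delta method or a parametric bootstrap. Require that the fitted curvature B2 + G2·s is negative in all three sessions; otherwise report the turning point as undefined and c(iv) as not evaluable. Report the turning point per session with its interval.

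Testing that the session 3 minus session 1 difference is below zero is an alternative, preferably by bootstrap: with a fixed peak and flattening curves, its delta-method test rejected in 4.1–4.8% against a nominal 2.5%, while D stayed at 2.3–2.7%.

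While this section is open, it would help to say what rising less sharply means in c(iii). The average slope over all 20 rises is sess:rise, as planned. The initial ascent, at rise 1 (1 − 10.5 = −9.5 from the centre), changes with session by G1 − 19·G2, and the test would be of that quantity below zero. This is a side remark and adds no weight to the point.

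The cost is a line of SAP wording and a few lines of code after the same model fit, plus a fresh check of whether 50 participants suffice for this contrast. Turning points will be imprecise wherever curvature is near zero.

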In order to prevent insufficient Power due to drop-outs, about 10% more participants should be surveyed. A total of 100 participants should therefore be surveyed (50 per group). If it is not possible to survey 100 participants, some of the analyses mentioned above can also be carried out with fewer participants and (as indicated) still enough Power.

5. Exploratory Analyses

- a. Exploratory Relationships:
 - i. More suggestible people report a higher perceived presence in the VR environment than less suggestible people (in both groups).
 - 1. Correlation test (correlation between suggestibility and average experience of presence)
 - ii. More suggestible persons in the experimental group report a higher subjective trance depth than less suggestible persons in the experimental group.
 - 1. Correlation test (correlation between suggestibility and mean trance depth of the experimental group)
- b. Exploratory Analyses:
 - i. We expect a reduction in fear of heights after each session.
 - 1. $\text{HIQ} \sim \text{grp} + \text{mtp} + \text{grp:mtp} + (1 | \text{id})$ (for all sessions)
 - a. mtp: measurement time point, pre vs. post per session
 - ii. We expect that the experimental group shows a lower level of fear of heights in the one-week follow-up than in the pre-measurement of the second session (one-week follow-up after one session). (no investigation of the control group)
 - 1. $\text{HIQ} \sim \text{follow} + (1 | \text{id})$
 - a. follow: pre second session vs. one-week follow-up
 - iii. We also plan to look at how many subjects in the experimental group continue to report a fear of heights below the cut-off for inclusion in the study (HIQ Score > 29) after three months.
- c. Checks:
 - i. We expect no difference in suggestibility between the groups.
 - 1. $\text{sugg} \sim \text{grp} + (1 | \text{id})$
 - ii. We expect no influence of suggestibility on the initial extent of fear of heights
 - 1. $\text{HIQ} \sim \text{sugg} + (1 | \text{id})$
 - iii. We expect no difference in the initial extent of fear of heights between the two groups.
 - 1. $\text{HIQ} \sim \text{grp} + (1 | \text{id})$

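### Hypothesis d(iii) predicts opposite suggestibility slopes in the two groups, but the only test named for it, `grp:sugg`, tests the difference between the slopes and not the sign of either.

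*SAP*

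**What the plan says.** SAP section 2, hypothesis d(iii), makes a separate statement about each group. For the experimental arm it expects that "in the experimental group participants with higher suggestibility show a lower level of anxiety experience during the height confrontation than less suggestible participants". For the control arm it expects the opposite: "but in the control group higher suggestible participants exhibit greater anxiety experience during the height confrontation than less suggestible participants". As slopes of fear on suggestibility, these are a negative slope in the experimental group and a positive slope in the control group.

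Section 3 sets the method for all hypotheses: "Each model is tested with the car::Anova() function (model comparison Typ II ANOVA) in R to determine the significance of the individual effects". Analysis d fits "fear ~ grp + sugg + sess + rise + rise^2 + grp:sugg + sess:rise + sess:rise^2 + (rise + rise^2 | id)", and its closing line assigns the test: "For hypothesis d(iii) we investigate the significance of grp:sugg". No per-group slope, sign check or contrast is attached to d(iii).

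On size, section 4 says that analysis d "needs 50 participants to achieve a Power of 80% for the effects of interest". It then sets the overall target: "A total of 100 participants should therefore be surveyed (50 per group)". The SAP states no alpha level, effect size or variance component.

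**The concern.** One number, the difference between two slopes, cannot fix the sign of both. A significant `grp:sugg` with the control slope above the experimental slope fits the predicted crossover. It fits equally well a flat control slope, or two negative slopes of which the control slope is the shallower.

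Most of the other group comparisons in the plan, a(ii), b, c(v) and d(ii), each state a single contrast between groups. Reading the direction of the matching term is enough for those. For d(iii) it is not, because its second half is a claim about the control group alone.

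At stake is a substantive statement about the control condition: that suggestible people do worse in it. Under the rule as written, the trial could report this when the control slope is zero or negative. The Type II table offers no substitute, because its `sugg` line is tested ignoring `grp:sugg` and is not the slope in either group.

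**Working it through.** **Plan's own figure.** The 50 participants for analysis d cannot be reproduced, because the SAP gives no alpha, effect size, SD or variance components. The point concerns decision logic and does not need that figure.

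**What the model contains.** The experimental group is the reference (section 3). Write b_E and b_C for the slopes of fear on suggestibility in the two groups.

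- coefficient of `sugg` = b_E
- coefficient of `grp:sugg` = b_C − b_E
- control slope = `sugg` + `grp:sugg` = b_C

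d(iii) asserts b_E < 0 and b_C > 0. The named test addresses only b_C − b_E = 0.

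**Illustration of size.** Assumed inputs, none from the SAP: two-sided 0.05, person-mean fear with SD 1 in each group, standardised suggestibility (so slope = correlation r), and equal groups. With n per group,

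SE(b_C − b_E) ≈ √{[(1 − r_E²) + (1 − r_C²)] / (n − 3)}, and z = (r_C − r_E) / SE.

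Example with n = 50, r_C = 0, r_E = −0.4: SE = √[(0.84 + 1)/47] = 0.198 and z = 0.4/0.198 = 2.02. P(significant) ≈ Φ(2.02 − 1.96) = 0.52.

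Simulation of the same regression (40,000 runs per cell), 50 per group, true control slope zero:

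| r_E | `grp:sugg` significant | significant and both estimated signs as predicted |
|---|---|---|
| −0.2 | 0.165 | 0.150 |
| −0.3 | 0.320 | 0.270 |
| −0.4 | 0.525 | 0.388 |
| −0.55 | 0.817 | 0.485 |

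If both slopes must be significant in the predicted directions, the crossover is confirmed in only 0.007 to 0.035 over the same range. With 25 per group, `grp:sugg` is significant in 0.104, 0.176, 0.286 and 0.503. With both slopes negative and 50 per group, it is significant in 0.330 (r_E −0.4, r_C −0.1) and 0.550 (−0.5, −0.1).

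A sign check helps only partly when the control slope is zero, because its estimate is then positive about half the time by chance.

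**Power of a two-slope rule.** Assume that `grp:sugg` has exactly 80% power at N = 50, and that the slopes are equal and opposite.

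- Noncentrality of `grp:sugg` at N = 50: 1.960 + 0.842 = 2.802.
- The SE of a slope difference is √2 times the SE of one slope. Each slope is half the difference, so each has noncentrality 2.802/√2 = 1.981.
- Power per slope at N = 50: Φ(1.981 − 1.960) = 0.508. Both: 0.508² = 0.258 (simulation with t tests 0.289).
- At N = 100 each slope has noncentrality 2.802 and power 0.80. Both: 0.80² = 0.64 (simulation 0.694).
- If the two slopes differ 3:1 in size, both are confirmed in 0.140 (N = 50) and 0.284 (N = 100).
- If about 10% drop out of 100, leaving 90 analysed, the symmetric case gives 0.757² ≈ 0.574.
- Joint power of 80% in the symmetric case needs about 132 analysed participants.

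**The case against.** The best defence is that section 3 names the term to be examined but does not say that a small p-value confirms the hypothesis. Section 2 fixes the direction in each group, d(iii) is itself phrased as an interaction, and the fitted model yields both slopes. An attentive analyst would look at them. This stands in part: no new model is needed, and a fully reversed pattern would contradict the preregistered direction, so it should not be counted as a likely false claim. It does not remove the gap. No stated rule uses the slopes, and looking only at the estimated signs still leaves 15 to 49% in the illustration.

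Four stronger readings are tempting and are not supported.

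- *The test is significant in 80% of trials at N = 50 and about 98% at N = 100 whether or not the crossover is true.* This holds the slope difference fixed, so equal power is true by construction. It also ties the 50 participants to `grp:sugg`, whereas section 4 gives that figure for all effects of interest in analysis d, which are seven terms. At the required difference of 0.858 residual SD, a flat control slope needs an experimental correlation of 0.858/√(1 + 0.858²) ≈ 0.65 in absolute size.
- *Every directional hypothesis in the SAP has this fault.* Where a hypothesis is a single contrast, an unsigned test read together with its estimate is sufficient.
- *Model d also fails question c, because it asks* "Does the anxiety experience curve change during the VR height confrontation over the three sessions in both groups" *and has no group-by-session or group-by-curve terms.* Hypotheses c(i) to c(iv) name no group, and section 5 uses the same phrase about both groups for a single pooled correlation.
- *The missing random session slope in model d is part of this problem.* It concerns the `sess` test, does not bear on the crossover, and belongs in a separate point.

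**Conclusion.** The point holds for d(iii) alone. The hypothesis claims two opposite slopes and the rule tests one difference. A significant `grp:sugg`, even with the expected sign, supports a lower slope in the experimental group; it does not support a positive slope in controls. This conclusion follows from the text and needs no assumption.

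The size does need assumptions. With a truly flat control slope, the illustrated risk of apparent support ranges from about one in six to about four in five, depending on an experimental slope that the SAP does not state. With a sign check, the upper end falls to about one in two. These figures show that the risk is not negligible; they do not predict this trial's error rate.

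The plan should be changed, but this is one sub-hypothesis and the planned model already supplies what is missing.

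**What to change.** Keep model d and the `grp:sugg` test, and choose one of two options in the SAP text.

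- **(a) Reword the hypothesis.** State d(iii) as a lower suggestibility slope in the experimental group than in the control group. Decide it on `grp:sugg` together with its sign, and report both simple slopes with confidence intervals. This costs only wording and loses no power, but the crossover is no longer claimed.
- **(b) Keep the crossover.** Claim it only if both simple slopes from model d differ significantly from zero in the predicted directions. On the assumption that `grp:sugg` has exactly 80% power at N = 50, a true symmetric crossover is then confirmed in only about 26 to 29% of trials at N = 50 and 64 to 69% at N = 100. It is confirmed less often if the slopes differ in size. The 80% power stated for 50 participants must not be claimed for this rule.

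Section 1 of the SAP says that no data have been collected, so either change can be made without hindsight. Option (a) is the cheaper; option (b) is justified only if the control-group claim matters in its own right.
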